5.7 Sample Size and Power

Forty individuals with ASD (aged 14 to 18 years) will be recruited. In each individual, baseline and post acute-dose imaging data will be obtained at three doses: (1) placebo, (2) STX209 15 mg, or (3) STX209 30 mg. Imaging measures at these three doses will be obtained at least 1 week apart, with the order of placebo and STX209 pseudo-randomized with the constraint that the STX209 15mg dose will be administered before the STX209 30 mg dose (FDA requirement). Assuming lost data or incomplete data sets from 4 individuals, the following power calculations were performed assuming a final sample of 36. As detailed in Section 1.3, given significant between subject variability in auditory cortex neural circuit pathology and thus potential between subject differences with regard to normalization of brain activity in response to STX209, the below statistical analyses conservatively assume a response to STX209 from approximately 50% of the participants. As detailed below, although the study is sufficiently powered to assess a baseline versus a 'general' post acute-dose change (i.e., averaging 15mg and 30mg), there is insufficient data to determine if the study is powered to observe a difference between STX209 15mg and STX209 30mg acute dose brain responses. As such, present data will provide preliminary data to guide future studies investigating STX209 dose differences.

Regarding the primary aims, assuming baseline to post acute-dose changes in M100 latency of approximately 2.5 ms (5 ms = one-half the ASD and control group differences reported in Roberts et al. (2010) and in the range observed in the single Arbaclofen study patient (2-8ms), but half of 5 ms given acute responses in only 50% of the participants), and assuming a standard deviation of similar size (which may be conservative given initial cross-dose averaging), and assuming a response in only 50% of the population, given a sample of 36 and $p = 0.05$, the power to detect a main effect on M100 latency is equal to 0.80. Assuming baseline to post acute-dose changes in post-stimulus gamma-band activity approximately half that reported in Edgar et al. (2015), the power to detect a main effect on gamma activity is approximately 0.70.

Given between subject variability in baseline auditory latency and gamma measures, and given a hypothesis that those participants showing the most pronounced M100 and gamma neural circuit pathology will show the largest response to STX209, the above analyses will be repeated with Group as a factor, with grouping obtained via a median split of M100 latency or gamma activity to identify those participants with more versus less auditory cortex neural circuit pathology. A Group X baseline to post acute dose interaction is expected, with significantly greater change observed in the more impaired ($N = \sim 18$) versus less impaired group ($N = \sim 18$). Given an expected greater effect in the participants showing greater impairment at baseline (e.g., a 5+ ms delay in the group showing greater auditory neural abnormalities), the study is powered at approximately 0.80 to observe an effect of this size.

Thus, the present study is sufficiently powered to assess the primary study aims.

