3.3.2 Total Number of Study Sites/Total Number of Subjects Projected

The study will be conducted at one investigative site in the United States – at the Children’s Hospital of Philadelphia. The clinical and neuropsychological testing will occur at the Roberts Pediatric Center at the Children’s Hospital of Philadelphia ([name]) or at Main Hospital or at Clinical and Translational Research Center at [name] and the medical evaluation on screening

visit and Visit 3 will occur either at the Clinical and Translational Research Center at [name], or at the main hospital at [name]. [name], M.D., a Developmental-Behavioral Pediatrician at the Children's Hospital of Philadelphia will be the primary physician on this project.

We will enroll 40 subjects in order to get 38 evaluable subjects.

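### The 0.80 power for M100 latency in section 5.7 does not follow from its stated inputs and does not cover the placebo comparison, so the closing claim about the primary aims goes further than the section shows

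*Combined protocol and SAP*

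**What the plan says.** Section 5.7 recruits 40, allows for 4 with lost or incomplete data, and states that "the following power calculations were performed assuming a final sample of 36". For M100 it takes a 5 ms effect and halves it to 2.5 ms because only half the participants are expected to respond. It then continues "and assuming a standard deviation of similar size (which may be conservative given initial cross-dose averaging", lists the 50% response a second time, and concludes that "the power to detect a main effect on M100 latency is equal to 0.80". The SD has no numerical value or source, and the test, its sidedness and any correlation between visits are not stated.

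The section says that this power relates to baseline versus post-dose with 15 mg and 30 mg averaged, and that there is too little information to judge power for 15 mg versus 30 mg. For gamma, "the power to detect a main effect on gamma activity is approximately 0.70", with no effect size or SD in numbers. It ends: "Thus, the present study is sufficiently powered to assess the primary study aims".

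Elsewhere, Objective 1 in section 2.1 asks for change against baseline and against placebo, and then about dose. Sections 5.4 and 5.6 treat gamma as primary alongside M100. On numbers, section 3.3.2 says "We will enroll 40 subjects in order to get 38 evaluable subjects", and the synopsis agrees with it.

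**The concern.** A change equal to its own standard deviation is a standardised effect of 1.0. With 36 paired observations, that gives power close to certainty, not 0.80. Either the SD used was not the one described, or the responder discount was applied twice, or the calculation was something the text does not describe. A reader cannot tell which.

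The choice matters because the placebo comparison is the one that separates a drug effect from repeat-scan and time-in-session effects, and its power depends heavily on that unstated SD. Someone relying on the closing sentence could treat a null active-versus-placebo result as informative when nothing in section 5.7 bears on it.

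**Working it through.** **Inputs from section 5.7:** change 2.5 ms; SD similar in size, read literally as 2.5 ms; n = 36; level 0.05. Two-sided testing is my assumption.

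**Step 1. Reproduce the stated figure.** Paired (one-sample) t-test on change scores: d = change/SD, noncentrality = d × √n, 35 degrees of freedom, exact noncentral t. With d = 2.5/2.5 = 1.0 and noncentrality 1.0 × 6 = 6, power is 0.9999. At d = 1.0, ten subjects would already give 0.80.

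**Step 2. Try other readings at n = 36.**

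| Reading | d | Power |
|---|---|---|
| SD 2.5 ms per scan, no pre/post correlation: SD of change 2.5 × √2 = 3.54 | 0.707 | 0.985 |
| Half respond by 5 ms, half by 0, residual SD 2.5: total SD √(2.5² + 2.5²) = 3.54 | 0.707 | 0.985 |
| Responder discount applied twice: 1.25/2.5 | 0.5 | 0.83 (one-sided 0.90) |
| SD taken as the 5 ms in the same sentence: 2.5/5 | 0.5 | 0.83 (one-sided 0.90) |

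None gives 0.80. Solving for it, d = 0.480, so SD = 2.5/0.480 ≈ 5.2 ms.

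**Step 3. Power for active minus placebo, which the plan does not give.** The contrast is the mean of the 15 mg and 30 mg changes minus the placebo change, taken as 2.5 ms (that is, no change on placebo). I assume equal variances and a common between-visit correlation r of the change scores. The documents give no r, so I show 0 to 0.5.

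- If the SD s describes a single-dose change, the contrast variance is s²[(1 + r)/2 + 1 − 2r] = 1.5 s²(1 − r).
- If s describes the dose-averaged change, the contrast variance is 3 s²(1 − r)/(1 + r).

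At s = 5.21 and r = 0, the contrast SDs are 5.21 × √1.5 = 6.38 and 5.21 × √3 = 9.02. At r = 0.5 they are 4.51 and 5.21.

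| SD (ms) | Per single-dose change, r = 0 to 0.5 | Dose-averaged change, r = 0 to 0.5 |
|---|---|---|
| 2.5 | 0.997 to >0.999 | 0.92 to >0.999 |
| 5 | 0.66 to 0.92 | 0.39 to 0.83 |
| 5.2 (back-solved) | 0.63 to 0.90 | 0.37 to 0.80 |

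**Step 4. Set the closing sentence against the section.** Gamma is primary and is given about 0.70. Power for 15 mg versus 30 mg is said to be undeterminable, although dose is part of Objective 1. Power against placebo is absent. Only baseline versus the 15/30 mg average on M100 is credited with 0.80.

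**Step 5. Evaluable n.** 40 − 4 = 36 in section 5.7, against 38 in the synopsis and section 3.3.2. At d = 0.48 this moves power only from 0.80 to 0.82.

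**The case against.** The strongest reply is that the discrepancy runs in the safe direction: the stated inputs give more power than is claimed. The wording is also loose. If the SD meant was near the 5 ms in the same sentence, power is 0.83, and a 5 ms difference between the two median-split groups (18 v 18) would also have 0.83, so one unstated SD roughly fits both 0.80 claims. The synopsis calls the study exploratory. Section 5.7 openly limits its power statement to baseline versus the averaged doses, which matches the first planned contrast in sections 5.6 and 5.6.2. The ANOVA has placebo as a dose level, so placebo is not missing from the analysis. Using 36 rather than 38 is the cautious choice.

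Most of this stands, and it rules out several stronger readings that a reader might infer:

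- *The study is underpowered.* The documents do not show this. At the literal SD the placebo contrast also has power of 0.92 or more.
- *Power against placebo is 0.37.* That needs the back-solved SD to describe the dose-averaged change and r to be 0. The remark in section 5.7 about cross-dose averaging may instead mean an SD not yet reduced by averaging, which gives 0.63 to 0.90.
- *The median split confirms 5.2 ms.* Section 5.7 states neither the between-group difference in change nor the test. Read as a within-group test with n = 18, 0.80 would imply an SD of about 7.1 ms.
- *Responder spread was ignored, so true power is about 0.71.* That figure uses √(5.2² + 2.5²) = 5.77 ms, which counts the spread twice if 5.2 ms is already the total SD.

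The reply does not restore the 0.80. Neither an SD of 5 ms nor a double discount gives exactly 0.80, and the text states neither. It also does not supply the missing power against placebo or support the closing sentence.

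**Conclusion.** The point holds as a fault in the stated figure and in the conclusion drawn from it. With a 2.5 ms change, an SD of 2.5 ms, n = 36 and a two-sided 0.05 level, power exceeds 0.999; reaching 0.80 takes an SD of about 5.2 ms. Whatever SD was used, the figure applies to change from baseline on the averaged active doses and says nothing about placebo. Power against placebo could lie anywhere from 0.37 to above 0.99, depending on the SD, what it describes and a between-visit correlation assumed here to be 0 to 0.5. The closing sentence is not supported for gamma at a conventional 0.80, for the dose comparison, or for the placebo part of Objective 1. The 36 versus 38 mismatch is minor. Whether the study has adequate power cannot be settled from the documents, and 5.2 ms should not be taken as an established SD, because it was obtained by solving backwards from 0.80.

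**What to change.** Revise section 5.7 and align the synopsis:

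1. State the SD of change actually used for M100, its source, whether it is per dose or dose-averaged, whether it includes the spread between responders and non-responders, and the test and its sidedness. State whether the 50% discount enters once. Recompute the M100 power from those inputs.
2. Add power for active minus placebo over a stated range of SD and between-visit correlation.
3. Give the gamma effect size and SD in numbers; keep 0.70 only if they are given and reproduce it.
4. Use one evaluable n in section 5.7, section 3.3.2 and the synopsis.
5. Limit the closing sentence to the comparisons calculated, and call 15 mg versus 30 mg exploratory.

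Do not insert 5.2 ms as the assumed SD unless a source supports it. The cost is text and a short recalculation, with no change in sample size or procedures. Some stated figures may become less favourable.

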	
use of a single averaged baseline measure). Contrasts of a priori interest assess (1) a baseline versus post-acute dose change in the dependent measures averaging across STX209 15 and 30 mg, as well as (2) a change in dependent measures from baseline versus STX209 15 mg versus STX209 30 mg, with this test demonstrating an effect of dose. Given the possibility of between-subject variability in the degree of baseline auditory neural pathology, analyses will also examine response to treatment in those participants showing the greatest baseline auditory neural circuit abnormality (median split on M100 latency or gamma power), with a larger effect of treatment expected in those participants showing greater baseline auditory neural impairment. Secondary and exploratory analyses examine baseline to post acute-dose response changes in MRS auditory GABA concentration as well as associations between MEG functional measures and MRS GABA concentration.

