Repetitive Behaviour Scale (RBS)		X			

Social Communication Questionnaire (SCQ)		X			
Social Responsive Scale (SRS-II)		X			
Vineland Adaptive Behaviour Scales (2 nd edition)		X			
Wechsler Abbreviated Scale of Intelligence (WASI-II)		X			
Randomization		X			
MEG Scan (pre/post drug administration)			X	X	X
MRI Scan			X	X	X
Dispense Study Drug			X	X	X
Adverse Event/Serious Adverse Event Assessment			X	X	X

NOTE: At each of the three visits, subjects will receive (in increasing order) doses of 15mg and 30mg of STX209 and a randomly administered single placebo exam. Each subject's participation will last approximately 3-4 weeks, although participation could be extended up to six or eight weeks if subjects are unable to come four consecutive weeks in a row. At each visit, baseline MEG will be obtained followed by acute single-dose drug/placebo administration, followed 60 minutes later by repeat MEG

*MEG Assessment visits will be scheduled no less than four days or more than 14 days apart.

** In cases where subject is unable to do a blood draw on the day of the screening visit due to anxiety/fear/discomfort if no medical risk factors are identified during medical history review, we will either accept BUN and Creatinine results from an outside source within 3 months of first imaging visit or attempt to do the blood draw on the day of the imaging visit

FIGURE 1: STUDY DIAGRAM

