5.6 Statistical Methods

Primary statistical analyses assess baseline versus post acute-dose (placebo, STX209 15 and 30 mg) changes for (1) M100 auditory latency, and (2) post-stimulus auditory gamma-band activity. For each dependent measure, ANOVAs with dose as a repeated measure will examine baseline versus post acute-dose changes (analyses showing no significant differences across time in baseline M100 and gamma measures will allow use of a single averaged baseline measure). Contrasts of *a priori* interest assess (1) a baseline versus post-acute dose change in the dependent measures averaging across STX209 15 and 30 mg, as well as (2) a change in dependent measures from baseline versus STX209 15 mg versus STX209 30 mg, with this test demonstrating an effect of dose. Secondary and exploratory analyses examine baseline to post acute-dose response changes in MRS auditory GABA concentration as well as associations between MEG functional measures and MRS GABA concentration.

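### The median-split test sets pre-dose MEG against change from that same pre-dose MEG without naming placebo, so regression to the mean biases the interaction in the predicted direction

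*Combined protocol and SAP*

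**What the plan says.** Section 5.7 (Sample Size and Power) divides subjects into more and less impaired halves, "with grouping obtained via a median split of M100 latency or gamma activity". The synopsis, under Statistical and Analytic Plan, confirms that the split is on pre-treatment values: it singles out participants "showing the greatest baseline auditory neural circuit abnormality (median split on M100 latency or gamma power"). Section 5.7 then predicts the result: "A Group X baseline to post acute dose interaction is expected, with significantly greater change observed in the more impaired" half. It assumes about 18 subjects per half and 5 ms or more in the more impaired half, and claims power of about 0.80.

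The note to Table 1 gives the only source of these values: "At each visit, baseline MEG will be obtained followed by acute single-dose drug/placebo administration". No MEG is scheduled at screening. The a priori contrast to be repeated with Group added is, in Section 5.6, "a baseline versus post-acute dose change in the dependent measures averaging across STX209 15 and 30 mg". Section 5.6 also permits pooling of baselines on a condition: "analyses showing no significant differences across time in baseline M100 and gamma measures will allow use of a single averaged baseline measure".

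Neither section says which baseline defines the split. Neither gives a reliability for M100 or gamma, an adjustment for regression to the mean, or a Group comparison of active with placebo.

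**The concern.** A measured baseline is a true value plus scan error. A subject whose M100 happens to read long at the pre-dose scan is more likely to fall in the more impaired half. The same error is then subtracted when his change is formed, so he appears to improve. A subject whose M100 reads short appears to worsen. For gamma the sign reverses and the logic is the same. The halves therefore differ in expected change without any drug effect, in the direction the plan predicts.

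The placebo session shows the same regression and is the natural control, but the named interaction does not call on it. A positive result would be read as support for the hypothesis that the most impaired participants respond most, and part of it could be artefact.

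**Working it through.** **The plan's power figure.** Inputs from Section 5.7: 18 v 18, 5 ms, alpha 0.05. Assumed: two-sided test, no change in the less impaired half. No SD is given for the interaction; for the main effect the plan assumes one of similar size to 2.5 ms. The noncentrality of the two-sample t test is (5/SD) × √(18/2) = 15/SD, on 34 df.

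- SD 2.5 ms: 6.0, power 1.00.
- SD 5 ms: 3.0, power 0.83.
- Power of 0.80 needs an SD of about 5.2 ms, which is not stated.

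The stated 0.80 is thus not reproduced exactly. The bias argument does not depend on it.

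**Expected gap with no drug effect.** Let e be the SD of single-scan error and b the between-subject SD, so reliability r = b²/(b² + e²). Reliability is not in the documents; 0.9 down to 0.5 is assumed. Errors are first taken as independent, and the SD of averaged change as 5 ms. For a classifying baseline with error variance v that is also the start of the change, the large-sample gap between halves is 2√(2/π) × v/√(b² + v), where 2√(2/π) = 1.596.

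*Same-visit baselines* (mean of the two active-visit scans): v = e²/2, and the variance of change is e²/2 + e²/2 = e², so e² = 25 and v = 12.5.
- r = 0.9, b² = 225: 1.596 × 12.5/√237.5 = 1.3 ms.
- r = 0.5, b² = 25: 1.596 × 12.5/√37.5 = 3.3 ms (3.2 by simulation with 36 subjects).

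*Pooled baseline* (mean of three): v = e²/3, and the variance of change is e²/2 + e²/3 = 5e²/6, so e² = 30 and v = 10.
- r = 0.9, b² = 270: 1.596 × 10/√280 = 0.95 ms.
- r = 0.5, b² = 30: 1.596 × 10/√40 = 2.5 ms.

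All gaps halve if the SD of change is 2.5 ms.

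**False-positive rate.** Simulation with no drug effect, 36 subjects, median split, two-sided 5% t test. The rate depends on reliability and not on the SD in ms, so it applies equally to gamma.

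| Baseline used for the split | r = 0.5 | 0.7 | 0.8 | 0.9 | 0.95 |
|---|---|---|---|---|---|
| Mean of two active visits, also used for change | 0.51 | 0.29 | 0.19 | 0.12 | 0.08 |
| Mean of three visits, also used for change | 0.32 | 0.18 | 0.13 | 0.09 | 0.07 |
| Visit 1 only, change from own-visit baseline | 0.19 | 0.13 | 0.10 | 0.08 | 0.06 |

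The excess rejections fall almost wholly in the predicted direction. If half the error variance is shared by the pre and post scans of a visit (also an assumption), the range over r = 0.9 to 0.5 is about 0.08 to 0.27 for the two-visit mean and 0.06 to 0.15 for the three-visit mean.

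**With placebo as control.** With the three-visit mean as classifier, testing active minus placebo gives 0.047 to 0.052 over r = 0.5 to 0.95 and a mean gap of about zero. A check with that mean as a continuous moderator, with independent or half-shared errors, gave 0.047 to 0.053.

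**Power after the change.** Independent errors, e = 5, a 5 ms difference, 18 v 18:
- Active change alone: SD 5, power 0.83.
- Active change minus placebo change: variance e² + 2e² = 3e², SD 8.7, power 0.39.
- Post-active minus post-placebo: variance e²/2 + e² = 1.5e², SD 6.1, power 0.66.

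**The case against.** Four points have force.

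1. *Placebo is in the model.* The ANOVA has dose as a repeated factor with placebo as a level, and Section 2.1 asks for comparison with placebo as well as baseline. A Group × dose × time term could be run. A reader might therefore infer that placebo is excluded outright; the documents do not show that. What stands is that the a priori contrasts and the interaction in Section 5.7 do not specify it.

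2. *The artefact is smaller than the planned effect.* A reader might infer that regression to the mean alone would deliver the expected result. It would not: gaps of about 0.9 to 3.2 ms fall short of 5 ms, and at reliability 0.95 the error rate is only about 6% to 8%.

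3. *The rates rest on unstated inputs.* Reliability and within-visit error correlation are assumed. Shared error lowers the rates, as does a Visit 1 split. Pooling the baselines also helps, but Section 5.6 makes it conditional and it does not remove the bias.

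4. *The analysis is peripheral.* The synopsis calls the study exploratory, the split is absent from Section 5.6, and no primary endpoint depends on it. Selecting patients for later trials on this result is not mentioned; Section 5.7 speaks only of guiding later work on dose differences. Even so, the analysis has a directional hypothesis and a power claim, placed just before the conclusion that the primary aims are adequately powered.

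**Conclusion.** The concern holds as a bias, not as a full explanation of the planned effect. As named, the interaction is pushed in the predicted direction whenever the pre-dose scan contains error, whether or not the drug works. Its error rate is above 5%, by an amount the documents do not allow one to fix: about 9% to 32% (pooled) or 12% to 50% (same-visit) over reliability 0.9 to 0.5 with independent errors, and about 6% to 15% or 8% to 27% with half the error variance shared within a visit. The gap in ms also depends on the SD of change: 0.9 to 3.2 ms at an assumed 5 ms, half that at the 2.5 ms used in Section 5.7 for the main effect. The artefact inflates error and exaggerates effect modification. The primary endpoints are unaffected.

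**What to change.** In Section 5.7 and the synopsis, before unblinding:

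- Define the moderator as each subject's mean of the three pre-dose baselines, used as a continuous variable. Keep the median split for display. Equal weight on the three visits matters: a Visit 1 baseline would not cancel fully, because Visit 1 is an active visit in two of the three dose orders.
- Test moderator × (active mean minus placebo), labelled as a subgroup analysis and kept out of the primary test. State whether the outcome is the difference in change scores or post-active minus post-placebo.
- Base it on subjects with all three visits, which matches the 36 assumed in Section 5.7.
- Remove the 0.80 power claim, or restate it for the placebo-controlled interaction with its SD and sidedness.

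No new data are needed. The cost is precision: under the assumptions above, power for a 5 ms difference falls from about 0.83 to about 0.39 with change scores, or about 0.66 with post-active minus post-placebo. Those figures are for an 18 v 18 split and should be disclosed.
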